9.4.4. Exploratory Endpoint(s)

The exploratory endpoints of the trial are:

- Time to the patient being prescribed and patient agrees to it, time to first receipt, time to first use, time to daily use, time to dependence and number used of any of the following DME items (manual wheelchair, power wheelchair, augmentative and alternative and augmentative communication device, NIV and/or gastrostomy tube) from randomization to the end of the 24-week double-blind, placebo-controlled period and to Week 48 as well as reasons to receive the above DME. Time to dependence for invasive ventilation will also be recorded. Definitions for patient being prescribed and agrees to it, first receipt, first use, daily use, and dependence for the DME items of interest can be found in the Study Manual.
- Change from baseline to Week 24 in the four subdomain scores of the ALSFRS-R
- Time spent in each MiToS stage and number of patients to transition stages from baseline to Week 24
- Change from baseline to Week 48 in ALSFRS-R total score
- Change from baseline to Week 48 in FVC
- Combined assessment of change in ALSFRS-R total score, time to dependence on assisted ventilation, and survival time up to Week 48

- Change from baseline to Week 24 in the mega-score of muscle strength measured by HHD in bilateral first dorsal interosseous muscles, abductor pollicis brevis muscles, and abductor digiti minimi muscles
- Change from baseline to Week 24 and Week 48 in the EQ-5D-5L
- Change from baseline to Week 24 and Week 48 in the VAS of EQ-5D
- Time from first hospitalization through Week 24 and through Week 48
- All above endpoints are also applied to the end of the study

The analyses of the exploratory endpoints are as follows:

Time-to-event analyses will be conducted for the endpoints of durable medical equipment items. A MMRM will be used to analyze endpoints of change from baseline to the specified time point. Descriptive statistics will be presented for time spent in each MiToS stage and transition of stages. A joint-rank test will be used to analyze the combined assessment of change in ALSFRS-R total score, time to dependence on assisted ventilation, and survival time up to Week 48.

In addition, the comparisons listed below may also be performed as exploratory analyses of 1) change of ALSFRS-R total score from baseline, 2) combined assessment of change of ALSFRS-R, dependence on assisted ventilation, and survival time, or 3) change of other measures (as appropriate):

- Compare changes from baseline to Week 24 between the reldesemtiv and placebo groups
- Compare changes from Week 24 to Week 48 between the early-start and delayed-start treatment groups
- Compare changes from baseline to Week 48 between the early-start and delayed-start treatment groups
- Compare changes from Week 24 to Week 48 versus those from baseline to Week 24 in the delayed-start group

9.4.5. Safety Analysis

Safety data will be analyzed descriptively in the safety analysis set, including all patients who take any amount of study drug.

9.4.5.1. Adverse Events

All AE terms will be coded using the Medical Dictionary for Regulatory Activities (MedDRA). Primary system organ class (SOC) and preferred term (PT) of the TEAEs will be tabulated by the early-start and delayed-start treatment groups and periods (placebo-controlled period and active drug period). TEAEs will also be summarized by severity and relationship to study drug. AEs that led to early discontinuation from treatment or the trial and events of special interest will be summarized. Listings will be presented for patients who discontinued due to TEAEs.

9.4.5.2. Serious Adverse Events

All SAEs and SAEs leading to treatment discontinuation or death will be summarized by system organ class, preferred term, treatment and overall, and by riluzole and edaravone use status at baseline. Listings will be presented for patients who died and/or experienced serious AEs.

9.4.6. Pharmacokinetic Endpoints

Plasma concentrations of reldesemtiv will be summarized using descriptive statistics including mean, standard deviation, geometric mean, coefficient of variation, median, and range. Geometric mean concentrations over time will be graphically displayed.

9.4.7. Patient Disposition

The number of patients who are randomized, who complete the planned treatment, and who prematurely discontinue from the planned treatment and/or the trial will be presented by study period, treatment group and overall. Reasons for premature discontinuation as recorded on the termination page of the CRF will be summarized overall and by randomized treatment and for each period separately.

9.4.8. Demographics and Other Baseline Characteristics

Patient demographics and other baseline characteristics will be summarized descriptively by treatment and overall. To assess the comparability of treatment groups, demographic and baseline characteristics will be compared between treatments for the FAS using Cochran-Mantel-Haenszel tests for binary categorical variables, van Elteren tests for ordinal categorical measures, or analysis of variance (ANOVA) for continuous variables, stratified by riluzole use/non-use, edaravone use/non-use.

9.4.9. Investigational Product Exposure

IP exposure will be summarized overall and by treatment and study period, including, total number of doses administered, total amount of drug administered, and the total duration of IP administration, defined as the date of the last dose minus the date of first dose + 1.

9.4.10. Concomitant Medications

Concomitant medications will be summarized and classified by drug class and preferred term using the World Health Organization (WHO) Drug Dictionary. The version of the WHO Drug Dictionary will be specified in the clinical study report.

9.4.11. Clinical Laboratory Parameters

Descriptive statistics for clinical laboratory values and changes from baseline at each protocol specified assessment time point will be presented.

9.4.12. Vital Signs

Descriptive statistics for vital signs and changes from baseline at each protocol specified assessment time point will be presented.

9.4.13. Electrocardiogram

Descriptive statistics for ECG parameters (eg, heart rate, PR interval, QRS interval, QT interval, and QTc interval [both Bazett's and Fridericia's corrections]) and changes from baseline at each protocol specified assessment time point will be presented.

9.5. Interim Analyses

Two interim analyses are planned for this trial. The interim analysis methods and the specifications of the data snapshots will be detailed in an interim analysis plan.

Twelve (12) weeks after approximately one-third or more of the planned sample size is randomized, the first interim analysis may be triggered. Its purpose is to determine if there is a lack of effect of reldesemtiv on the ALSFRS-R in CY 5031, a finding that would be inconsistent with the prior observed effect on the change from baseline at 12 weeks in ALSFRS-R total score in the Phase 2 trial, CY 5022. At this interim analysis, the Data Monitoring Committee (DMC) will receive unblinded efficacy data from the independent, third-party biostatistical group supporting them and assess the effect of reldesemtiv on the change from baseline to Week 12 in the ALSFRS-R total score. At this interim assessment, if the treatment difference for change from baseline to Week 12 in ALSFRS-R total score has a one-sided p-value larger than or equal to 0.5 (ie, the estimated treatment difference of the change from baseline at Week 12 in ALSFRS-R total score is favoring placebo), the DMC may recommend stopping the trial due to futility. This futility analysis based on the data of change from baseline to Week 12 in ALSFRS-R will not have any alpha spending. The Sponsor will monitor the blinded aggregate standard deviation of the change from baseline to Week 12 in ALSFRS-R total score periodically and possibly adjust the specified alpha before this interim analysis is conducted.

Twenty-four (24) weeks after at least one-third of the planned sample size is randomized; the second interim analysis will be triggered. The goal of the second interim analysis is to evaluate whether the proposed Phase 3 trial has adequate power to achieve a statistically significant effect on the primary endpoint in the final primary analysis, given the planned enrollment, or if continuing the trial is futile. At this interim analysis, the DMC will receive unblinded efficacy data from the independent, third-party biostatistical group supporting them and assess the effect of reldesemtiv on the primary endpoint. In terms of futility, the DMC may recommend stopping the trial if the conditional power (CP) is less than 0.10. The futility boundary is non-binding. The DMC is to make a recommendation to stop the trial using their collective judgment and the totality of evidence available. The DMC may consider the first secondary endpoint in a similar fashion.

If the CP of primary endpoint is within a pre-specified promising zone from 0.40 to 0.90, the DMC may recommend increasing the sample size by 150 unless there is any safety concern or other concerns that preclude the recommendation. This method is referred to as the CDL adaptive method and was initially proposed by Chen, DeMets, and Lan (2004) as later extended by Gao, Ware and Mehta (2008) and Mehta and Pocock (2011) ([Chen 2004](#); [Gao 2008](#); [Mehta 2011](#), respectively). It is used to control type-1 error for sample size increase based on unblinded interim data. Within the pre-specified promising zone and a pre-specified fixed **increase** of the sample size, the CDL method could allow the final analysis to include all data before and after the interim look without inflating the type-1 error. This interim analysis will spend a very small 2-sided alpha of 0.0001 for the primary endpoint as well as all individual secondary endpoints.

The DMC is also expected to recommend stopping this trial due to superiority if a two-sided p-value is \leq alpha of 0.0001 for the primary endpoint as well as all individual secondary endpoints. Therefore, the significance level of 2-sided alpha of 0.0499 would be used for the final analyses for the primary endpoint and all individual secondary endpoints to control familywise error rate at overall alpha of 0.05.

9.6. Data Monitoring Committee

An unblinded DMC will review the planned unblinded interim analysis results to be provided by an independent, third-party biostatistical group and make recommendations as to stop or continue the trial. The DMC may also provide recommendation(s) on the trial conduct. In addition, the DMC will review regularly the emerging data for safety monitoring purpose. The DMC or Cytokinetics can require an ad hoc DMC meeting at any time. No study activities will be suspended during the safety review.

10. SUPPORTING DOCUMENTATION AND OPERATIONAL CONSIDERATIONS

10.1. Appendix 1: Regulatory, Ethical, and Study Oversight Considerations

10.1.1. Regulatory and Ethical Considerations

This trial will be conducted in accordance with the protocol and with the following:

- Consensus ethical principles derived from international guidelines including the Declaration of Helsinki and Council for International Organizations of Medical Sciences (CIOMS) International Ethical Guidelines
- Applicable ICH Good Clinical Practice (GCP) Guidelines
- Applicable laws and regulations

The protocol, protocol amendments, ICF, IB, and other relevant documents (eg, advertisements) must be submitted to an IRB/IEC by the investigator and reviewed and approved by the IRB/IEC before the trial is initiated.

Any amendments to the protocol will require IRB/IEC approval before implementation of changes made to the trial design, except for changes necessary to eliminate an immediate hazard to patients.

The investigator will be responsible for the following:

- Providing summaries of the status of the trial to the IRB/IEC annually or more frequently in accordance with the requirements, policies, and procedures established by the IRB/IEC
- Notifying the IRB/IEC of SAEs or other significant safety findings as required by IRB/IEC procedures
- Providing oversight of the conduct of the trial at the site and adherence to requirements of 21 CFR, ICH guidelines, the IRB/IEC, European regulation 536/2014 for clinical studies (if applicable), and all other applicable local regulations

10.1.2. Financial Disclosure

Investigators and sub-investigators will provide Cytokinetics with sufficient, accurate financial information as requested to allow Cytokinetics to submit complete and accurate financial certification or disclosure statements to the appropriate regulatory authorities. Investigators are responsible for providing information on financial interests during the course of the trial and for 1 year after completion of the trial.

10.1.3. Informed Consent Process

The investigator or his/her representative will explain the nature of the trial to the patient or his/her legally authorized representative and answer all questions regarding the trial.

Patients must be informed that their participation is voluntary. Patients must be able to comprehend and be willing to sign a statement of informed consent that meets the requirements of 21 CFR 50, local regulations, ICH guidelines, Health Insurance Portability and Accountability Act (HIPAA) requirements, where applicable, and the IRB/IEC or study center.

The medical record must include a statement that informed consent was obtained before any study-specific activities/procedures were performed and the date the consent was obtained. The authorized person obtaining the informed consent must also sign the ICF.

Patients must be re-consented to the most current version of the ICF(s) during their participation in the trial.

A copy of the ICF(s) must be provided to the patient or the patient's legally authorized representative.

10.1.4. Data Protection

Patients will be assigned a unique identifier by Cytokinetics. Any patient records or datasets that are transferred to Cytokinetics will contain the identifier only; patient names or any information which would make the patient identifiable will not be transferred.

The patient must be informed that his/her personal study-related data will be used by Cytokinetics in accordance with local data protection law. The level of disclosure must also be explained to the patient who will be required to give consent for their data to be used as described in the ICF.

The patient must be informed that his/her medical records may be examined by Clinical Quality Assurance auditors or other authorized personnel appointed by Cytokinetics, by appropriate IRB/IEC members, and by inspectors from regulatory authorities.

10.1.5. Committees Structure

The study organization will include an Executive Committee (EC), Steering Committee (SC) and DMC.

The EC will contribute to trial design, implementation, data analysis, and communication of trial results and will consist of experts external to Cytokinetics who are qualified by their medical and scientific expertise and experience. The responsibilities of the EC will be described in an EC charter.

The SC will contribute to implementation of the trial, data analysis, and communication of trial results. The SC members will be ALS experts external to Cytokinetics and represent the different geographies the trial will be conducted in. The responsibilities of the SC will be described in a SC charter.

The DMC will be established and be responsible for periodic review of study data to ensure the safety of patients, and for review of SAEs on an ongoing basis. The DMC will include external experts with relevant expertise, including a neurologist(s) specializing in ALS, statistician, hepatologist and nephrologist eg, representing clinical science and biostatistics. The independent DMC membership will exclude the individuals from Cytokinetics or the study team involved in trial conduct. The DMC members will have access to treatment assignments and patient level data from the clinical trial database. DMC membership, responsibilities, relationship with

Cytokinetics, and the purpose and timing of the meetings will be further described in the DMC charter.

10.1.6. Data Quality Assurance

All patient data relating to the trial will be recorded on printed or electronic CRF unless transmitted to Cytokinetics or designee electronically (eg, laboratory data). The investigator is responsible for verifying that data entries are accurate and correct by physically or electronically signing the CRF.

The investigator must maintain accurate documentation (source data) that supports the information entered in the CRF.

The investigator must permit trial-related monitoring, audits, IRB/IEC review, and regulatory authority inspections and provide direct access to source data documents.

Monitoring details describing strategy (eg, risk-based initiatives in operations and quality such as Risk Management and Mitigation Strategies and Analytical Risk-Based Monitoring), methods, responsibilities and requirements, including handling of non-compliance issues and monitoring techniques (central, remote, or on-site monitoring) are provided in the Monitoring Plan.

Cytokinetics or designee is responsible for the data management of this trial including quality checking of the data.

Cytokinetics assumes accountability for actions delegated to other individuals (eg, CROs).

Study monitors will perform ongoing source data verification to confirm that data entered into the CRF by authorized site personnel are accurate, complete, and verifiable from source documents; that the safety and rights of patients are being protected; and that the trial is being conducted in accordance with the currently approved protocol and any other trial agreements, ICH GCP, and all applicable regulatory requirements.

Records and documents, including signed ICFs, pertaining to the conduct of this study must be retained by the investigator in accordance with the strictest regulation applicable to this study and as obligated by the clinical trial agreement. No records may be destroyed during the retention period without the approval of Cytokinetics. No records may be transferred to another location or party without notification to Cytokinetics.

10.1.7. Source Documents

Source documents provide evidence for the existence of the patient and substantiate the integrity of the data collected. Source documents are filed at the investigator's site.

Data reported in the CRF or entered in the CRF that are transcribed from source documents must be consistent with the source documents or the discrepancies must be explained. The investigator may need to request previous medical records or transfer records, depending on the trial. Also, current medical records must be available.

10.1.8. Study and Site Start and Closure

The trial start date is the date on which the clinical trial will be open for recruitment of patients.

The first act of recruitment is the first site activated.

Cytokinetics or designee reserves the right to close the study site or terminate the trial at any time for any reason at the sole discretion of Cytokinetics. Study sites will be closed upon trial completion. A study site is considered closed when all required documents and study supplies have been collected and a study site closure visit has been performed.

The investigator may initiate study site closure at any time, provided there is reasonable cause and sufficient notice is given in advance of the intended termination.

Reasons for the early closure of a study site by Cytokinetics or investigator may include but are not limited to:

- Failure of the investigator to comply with the protocol, the requirements of the IRB/IEC or local regulatory authorities, Cytokinetics's procedures, or GCP guidelines
- Inadequate recruitment of patients by the investigator
- Discontinuation of further IP development

If the trial is prematurely terminated or suspended, Cytokinetics shall promptly inform the investigators, the IECs/IRBs, the regulatory authorities, and any CRO(s) used in the trial of the reason for termination or suspension, as specified by the applicable regulatory requirements. The investigator shall promptly inform the patient and should assure appropriate patient therapy and/or follow-up.

10.2. Appendix 2: Clinical Laboratory Tests

The tests detailed in [Table 9](#) will be performed by the central laboratory.

Local laboratory testing may be used only if central laboratory testing is not feasible. If local testing is conducted, it is important that the sample for central analysis is obtained at the same time, if feasible.

Protocol-specific requirements for inclusion or exclusion of patients are detailed in [Section 5](#) of the protocol.

Additional tests may be performed at any time during the trial as determined necessary by the investigator or required by local regulations.

Table 9: Protocol-Required Safety Laboratory Assessments

Chemistry		Urinalysis	Hematology	Other Assessments
Sodium	Total bilirubin	Specific gravity	Hemoglobin	TSH at screening
Potassium	Direct bilirubin	pH	Hematocrit	
Gamma-glutamyl transferase	Indirect bilirubin	Blood	RBC	Serum Beta Human Chorionic Gonadotropin ²
Chloride	CK	Protein	RDW	FSH ³
Calcium	ALP	Glucose	MCV	
Magnesium	LDH	Bilirubin	MCH	
Phosphorus	AST (SGOT)	UPCR	MCHC	
Urea nitrogen	ALT (SGPT)	Microscopy	WBC	
Creatinine ¹	Cystatin C ¹		Platelets	
eGFR _{Cr} ¹ (calculated using the CKD-EPI creatinine equation)	eGFR _{CysC} ¹ (calculated using the CKD-EPI cystatin C equation)			
Glucose	Uric acid			
Total protein	Albumin			
Cholesterol	Triglycerides			
Bicarbonate				

ALP = alkaline phosphatase; CK = creatine kinase; FSH = follicle-stimulating hormone; LDH = lactic acid dehydrogenase; MCH = mean corpuscular hemoglobin; MCHC = mean corpuscular hemoglobin concentration; MCV = mean corpuscular volume; RBC = red blood cell; RDW = red cell distributions width; SGOT = serum glutamic-oxaloacetic transaminase; SGPT = serum glutamic-pyruvic transaminase; WBC = white blood cell; TSH = Thyroid Stimulating Hormone; UPCR=urine protein creatinine ratio

Investigators must document their review of each laboratory report.

Laboratory results that could unblind the trial will not be reported to sites or other blinded personnel until the trial has been unblinded.

1= Sites blinded to results

2= Pregnancy test is required for WOCBP (see Appendix 3 [[Section 10.3](#)]);

3= FSH only at Screening to confirm menopausal status if patient age < 55 years and spontaneous menses within the past 1 year but currently amenorrheic (eg, spontaneous or secondary to hysterectomy) to confirm FSH levels > 40 IU/L.

10.3. Appendix 3: Contraceptive Guidance

Definitions:

Woman of Childbearing Potential

A woman is considered fertile following menarche and until becoming post-menopausal unless permanently sterile (see below).

If fertility is unclear (eg, amenorrhea in adolescents or athletes) and a menstrual cycle cannot be confirmed before first dose of study drug, additional evaluation should be considered.

Women in the following categories are not considered WOCBP:

1. Premenarchal
2. Premenopausal with 1 of the following:
 - Documented hysterectomy
 - Documented bilateral salpingectomy
 - Documented bilateral oophorectomy

For individuals with permanent infertility due to an alternate medical cause other than the above (eg, Mullerian agenesis, androgen insensitivity), investigator discretion should be applied to determining trial entry.

Note: Documentation can come from the site personnel's review of the patient's medical records, medical examination, or medical history interview.

3. Postmenopausal
4. Menopause is defined as:
 - ≥ 12 months of spontaneous and continuous amenorrhea in a female ≥ 55 years old; or
 - no spontaneous menses for at least two years in a female < 55 years old; or
 - age < 55 years and spontaneous menses within the past 1 year but currently amenorrheic (eg, spontaneous or secondary to hysterectomy) and with follicle-stimulating hormone (FSH) levels > 40 IU/L, or postmenopausal estradiol levels (< 5 ng/dL), or according to the definition of "postmenopausal range" for the laboratory involved

Highly Effective Method of Contraception

A highly effective method of contraception is one that has a failure rate of $< 1\%$ per year when used consistently and correctly.

Examples of highly effective contraception that have low user dependency are:

- Implantable progestogen-only hormone contraception associated with inhibition of ovulation
- Intrauterine device (IUD)

- Intrauterine hormone-releasing system (IUS)
- Bilateral tubal occlusion
- Vasectomized partner, only when the absence of sperm has been confirmed and vasectomized partner is the sole sexual partner of the female patient

Examples of highly effective contraception that are user-dependent are:

- Combined hormonal methods of birth control include oral, intravaginal, transdermal, injectable, or implantable
- Oral or injectable progestogen-only hormone contraception associated with the inhibition of ovulation
- Sexual abstinence

Note: Sexual abstinence is considered a highly effective method only if defined as refraining from heterosexual intercourse during the entire period of risk associated with the study drug. The reliability of sexual abstinence needs to be evaluated in relation to the duration of the trial and the preferred and usual lifestyle of the patient. Periodic abstinence (calendar, symptothermal, post-ovulation methods), withdrawal (coitus interruptus), spermicides only, and lactational amenorrhoea method (LAM) are not acceptable methods of contraception.

Contraception Guidance:

Women of Childbearing Potential

WOCBP must use at least one highly effective method of birth control. If a user-dependent, hormonal form of contraception is used as a highly effective method of birth control, a male condom must also be used. Male condom and female condom should not be used together (due to risk of failure with friction).

WOCBP should refrain from donating ova/eggs at least 10 weeks after the last dose of study drug.

If additional medications are given during treatment, the investigator is to review the prescribing information/summary of product characteristics for all concomitant therapy, as they may alter the contraceptive requirements. These additional medications may require an increase in the number of contraceptive methods and/or length of time that contraception is to be utilized after the last dose of protocol-required therapies. The investigator is to discuss these changes with the patient.

10.4. Appendix 4: Common Medications and Foods that Inhibit or Induce CYP3A4 or are OCT1/OCT2 Substrates

CYP3A4 Inhibitors	CYP3A4 Inducers
Strong Inhibitors: (Avoid)	Strong Inducers: (Avoid)
indinavir	avasimibe
nelfinavir	carbamazepine
ritonavir	phenobarbital
clarithromycin	phenytoin
itraconazole	St. John's Wort
nefazodone	rifampin
ketoconazole	rifabutin
grapefruit	
Seville oranges	
Moderate Inhibitors: (Use with caution)	Moderate Inducers: (Use with caution)
erythromycin	bosentan
diltiazem	efavirenz
verapamil	etravirine
suboxone	modafinil
	nafcillin
	nevirapine
	glucocorticoids (systemic)
Weak Inhibitors:	Weak Inducers:
cimetidine	amprenavir
	aprepitant
	armodafinil
	echinacea
	pioglitazone
	prednisone
	rufinamide
	clobazam
	lesinurad

OCT1 Substrates (Avoid)	OCT2 Substrates (Avoid)
oxaliplatin	pindolol
dofetilide	varenicline
	pilsicainide
OCT1 Substrates (Use with Caution)	OCT2 Substrates (Use with Caution)
aciclovir	metformin
ganciclovir	

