1=Remote visit lab draw only (no phone call) at Week 2 and Week 26; all other remote visits include video call and home lab draw

2= During the interval between the time of signing the informed consent form and immediately before the first dose of study drug, serious adverse events considered by the investigator to be related to study protocol-mandated procedure should be collected in the AE CRF. All other medical conditions should be collected as medical history prior to the first dose of study drug.

3=Clinical safety labs to include:

Chemistry: sodium, potassium gamma-glutamyl transferase, chloride, calcium, magnesium, phosphorus, urea nitrogen, creatinine, eGFR_{Cr} (calculated using CKD-EPI creatinine equation), Total protein, cholesterol, bicarbonate, total bilirubin, direct bilirubin, indirect bilirubin, CK, ALP, LDH, AST (SGOT), ALT (SGPT), Cystatin C, eGFR_{CysC} (calculated by CKD-EPI cystatin C equation), uric acid, albumin, triglycerides, glucose

Hematology: hemoglobin, hematocrit, RBC, RDW, MCV, MCH, MCHC, WBC, platelets

Urinalysis: specific gravity, pH, blood, protein, glucose, bilirubin, UPCR and microscopy

TSH at screening; bHCG as applicable for WOCBP, FSH as required to determine menopausal status at Screening per Appendix 3 ([Section 10.3](#))

4=PK sample at Week 4, Week, 12, and Week 24 at pre-dose and 2-4 hrs post-dose

5=PK samples at Week 36 for Sub-Study at pre-dose and at 0.5, 1, 2, 3, 4 and 6 hrs post-dose

6=Biomarker samples at Day 1 pre-dose and Week 24 pre-dose

7=Additional testing to be conducted if AEs of special interest are not resolved at the 4-week FU visit

8= Refer to [Section 8.1.2](#) for details of timing of home spirometry relative to FVC performed at in-clinic visits

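### One postmenopausal laboratory value exempts a recently menstruating woman under 55 from contraception and from the pregnancy tests at Day 1, Week 24 and Week 48

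*Protocol*

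**What the plan says.** Protocol Section 10.3 (Appendix 3) gives three ways to be menopausal, and a menopausal woman is not a WOCBP.

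- Age 55 or over: at least "12 months of spontaneous and continuous amenorrhea in a female" of that age.
- Under 55, on history alone: "no spontaneous menses for at least two years in a female < 55 years old".
- Under 55, on a laboratory value: "age < 55 years and spontaneous menses within the past 1 year but currently amenorrheic", with FSH above 40 IU/L, or an estradiol in the postmenopausal range, or a value in the laboratory's own postmenopausal range. The three are joined by 'or', so one is enough.

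Table 9 footnote 3 (Section 10.2) repeats the third rule and limits the measurement: "FSH only at Screening to confirm menopausal status if patient age < 55 years and spontaneous menses within the past 1 year". Footnote 3 of the Schedule of Activities (Section 1.3) provides for "FSH as required to determine menopausal status at Screening per Appendix 3". Estradiol is in neither list of laboratory tests, so FSH is the route that the trial actually equips.

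The mandatory safeguards depend on WOCBP status. Inclusion criterion 113 admits a woman who is not a WOCBP without contraception, and requires only a WOCBP to have a negative test within 3 days before the first dose. The pregnancy-test row of the Schedule of Activities is restricted to WOCBP. The contraception guidance reads "WOCBP must use at least one highly effective method of birth control".

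**The concern.** The three rules are out of order. Among women with the same postmenopausal value, the only group that the value releases is the one under 55 with menses in the past year. A woman of the same age who has gone longer without menses, 12 to under 24 months, stays a WOCBP. So does a woman of 55 or over at under 12 months. The documents give no reason for this.

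What is at stake is fetal exposure. A woman in the released group can take study drug for 48 weeks with no contraception required and without the pregnancy tests that a WOCBP has. Yet Section 8.3.1.10 stops study drug in a patient who becomes pregnant and requires a report within 24 hours.

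**Working it through.** The plan gives no figure to reproduce here. The check is of rule logic and simple counts.

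**Classification.** Take women who are currently amenorrhoeic and not permanently sterile. Cross age (2 groups), time since last menses (3) and a qualifying laboratory value (yes or no): 2 × 3 × 2 = 12 cells.

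| Age | Months since last menses | With value, as written | With value, third bullet deleted | Without value (both) |
|---|---|---|---|---|
| <55 | <12 | **not WOCBP** | **WOCBP** | WOCBP |
| <55 | 12 to <24 | WOCBP | WOCBP | WOCBP |
| <55 | ≥24 | not WOCBP | not WOCBP | not WOCBP |
| ≥55 | <12 | WOCBP | WOCBP | WOCBP |
| ≥55 | 12 to <24 | not WOCBP | not WOCBP | not WOCBP |
| ≥55 | ≥24 | not WOCBP | not WOCBP | not WOCBP |

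Deleting the bullet changes 1 of 12 cells, towards protection. No cell moves the other way.

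**Pregnancy tests.** The Schedule of Activities marks Screening, Day 1, Week 24 and Week 48, which is 4 tests. Appendix 3 treats a woman as fertile until she is shown to be postmenopausal. The FSH that would show it is itself drawn at Screening and run by the central laboratory. Unless she brings an earlier value, she is still presumed a WOCBP when the Screening test falls due. The secure loss is therefore 4 − 1 = 3 scheduled tests. The test within 3 days before the first dose (criterion 113) is also not required. I do not count it separately, because the Day 1 test can serve for it.

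**Contraception.** Criterion 113 requires it of a WOCBP during the study and for 4 weeks after the last dose. For a woman who completes dosing that is 48 + 4 = 52 weeks. As written, the exempted woman has 0 of 52; with the bullet deleted, 52 of 52.

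**Who is exempt by another route.** The bullet offers hysterectomy as an example of amenorrhoea. Such a woman is already exempt under category 2 ("Documented hysterectomy"), and Appendix 3 accepts a medical history interview as documentation. Permanent infertility from another medical cause is left to investigator discretion. Neither group needs the third bullet.

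**The case against.** The best defence is that the bullet asks for current amenorrhoea and laboratory evidence, and that the investigator is not passive. The note to criterion 113 makes the investigator responsible for reviewing menstrual history and recent sexual activity, and that duty is not confined to WOCBP. Appendix 3 suggests further evaluation where fertility is unclear. Section 10.2 adds: "Additional tests may be performed at any time during the trial as determined necessary by the investigator". These are real partial safeguards. None of them obliges anyone to test or to start contraception, and the note is directed at a pregnancy already present at entry.

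Two stronger readings are tempting, and the documents support neither.

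- A reader might infer that the woman misses all four scheduled tests. The timing of the FSH result makes that unsafe to claim for Screening.
- A reader might infer that she is fixed as postmenopausal for the whole trial. Nothing freezes the status. If her menses return she is no longer amenorrhoeic, no longer meets the bullet, and is a WOCBP by the default definition. A sentence on returning menses is therefore a clarification.

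It can also be said that the natural cure for a missing minimum duration is to add one, for example at least 12 months plus FSH. That would protect women at 1 to 11 months, but it would release women under 55 at 12 to 23 months with a qualifying value, who are protected now. Deletion takes protection from nobody.

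Finally, the documents give neither the number of such women nor their chance of pregnancy. That limits the weight of the point but does not explain the ordering of the rules.

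**Conclusion.** The point holds as a minor safety weakness. For a woman under 55 with menses in the past year, current amenorrhoea and one qualifying value, the written rule removes 52 weeks of required contraception, the required negative test before the first dose, and the scheduled tests at Day 1, Week 24 and Week 48.

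This assumes that she completes dosing, is not permanently sterile and brings no earlier laboratory value to Screening. The case rests on the internal ordering of the three rules, not on any outside estimate of fertility at a given FSH. The group is probably small, though the documents do not size it. The rule for women under 55 at 12 to under 24 months is not in question. Efficacy, alpha and power are unaffected. I would label this a cheap improvement.

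**What to change.** 1. In Appendix 3, delete the third menopause bullet.
2. Delete what then has no use: the FSH entry and footnote 3 in Table 9, and the FSH clause in footnote 3 of the Schedule of Activities.
3. As a clarification, add to Appendix 3 that a woman classed as postmenopausal whose menses return is a WOCBP from that date, with a pregnancy test then and at the remaining scheduled time points, and contraception per criterion 113.

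Keeping the bullet and adding a sentence that overrides it for women with menses in the past 12 months is not a sound alternative. Appendix 3 would then hold two opposing rules, and the retained FSH would decide nothing.

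Cost: a few more women under 55, some of them truly postmenopausal, have the scheduled pregnancy tests and use contraception, with a condom for the male partner under criterion 113. Abstinence as Appendix 3 defines it is accepted. The edit is short, but it needs a protocol amendment with IRB/IEC approval (Section 10.1.1) across about 85 sites, and updated consent text with re-consent (Section 10.1.3). It could travel with the next amendment.
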